2. ABBREVIATIONS AND DEFINITIONS

%CV	Coefficient of Variation calculated using $100 \times \sqrt{e^{s^2} - 1}$, where s^2 is the variance of the log transformed data
AE	Adverse event
ATC	Anatomic Therapeutic Code
CRF	Case report form
ED	Emergency Department
GCP	Good clinical practice
IEC	Independent ethics committee
kg	kilogram
MA	marketing authorisation
mg	milligram
µg	microgram
MHRA	Medicines & Healthcare products Regulatory Agency
ml	millilitre
µl	microlitre
PASS	Post Authorisation Safety Study
SAE	Serious adverse event
SmPC	Summary of Product Characteristics
TEAE	Treatment emergent adverse event
WHO	World Health Organisation

Date at which a study commences: Date of the start of data collection.

Start of data collection: The date from which information on the first study subject is first recorded in the study dataset.

End of data collection: The date from which the analytical dataset is completely available.

Analytical dataset: The minimum set of data required to perform the statistical analyses leading to the results for the primary objective(s) of the study.

Substantial amendment to the study protocol: Amendment to the protocol likely to have an impact on the safety, physical or mental well-being of the study participants or that may affect the study results and their interpretation, such as changes to the primary or secondary objectives of the study, to the study population, to the sample size, to the definitions of the main exposure, outcome and confounding variables and to the analytical plan.

4. ABSTRACT

TITLE	A Multicentre, Non-interventional, Prospective, Observational Drug Utilisation Study of Ayendi Nasal Spray Prescribed as Treatment in Emergency Departments in the United Kingdom (UK)
STUDY NUMBER:	DIA003
FINAL PROTOCOL DATE:	Draft 3.0 Dated 23/11/2016
PHASE:	IV – Post authorisation safety study (PASS) Drug Utilisation Study (DUS)
SPONSOR:	Wockhardt UK Limited
CHIEF INVESTIGATOR/ STUDY SITES:	Chief Investigator: [name] Emergency Department, North Bristol NHS Trust, [name] [contact] Email: [contact] Principal Investigators: Principal investigators will be recruited from a wide range of hospital EDs to include teaching and non-teaching hospitals, geographical coverage across the UK, department size, experience with diamorphine, and combined or separate paediatric EDs. Investigators may be physicians, nurse practitioners or suitably experienced researchers. Qualification of all investigators will be documented.
RATIONALE AND BACKGROUND	On review of the marketing authorisation application for Ayendi Nasal Spray by MHRA, it was noted that the safety study (DIA002) highlighted difficulties of administering the product in the Emergency Department (ED). This post-authorisation safety study (PASS), DIA003, was requested by MHRA to evaluate the practical usage of the product as a treatment in the ED. The study will assess the patterns of use particularly in relation to aspects that may have an impact on the safety of the product (e.g. co-medication [including other

	
opioids], medication errors). The study will also assess the effectiveness of risk minimisation activities.
 
The study is observational with no intervention.

RESEARCH QUESTION	To evaluate the practical usage of Ayendi Nasal Spray as a treatment post marketing in UK EDs.
OBJECTIVES:	
The following information will be collected and evaluated:
 
 ▶ Administration setting ▶ Patient characteristics ▶ Dose administered (to evaluate deviations from the prescribing and dosing instructions in the approved Summary of Product Characteristics) ▶ How prescribed and administered, (to evaluate if there are any differences in drug utilisation between the hospitals and prescribers) ▶ Adverse events ▶ Concomitant medication 
The study will assess patterns of drug utilisation with respect to aspects that may have an impact on its safety (e.g. co-medication [including other opioids], medication errors) and evaluate the effectiveness of risk minimisation activities.

STUDY DESIGN:	
Observational Model: Case-Only
 
Time Perspective: Prospective.

STUDY SIZE:	
A minimum of 400 patients will be recruited from EDs across a minimum of 20 hospitals (from a wide variety with respect to teaching and non-teaching hospitals, geographical coverage across the UK, department size, experience with diamorphine, and combined or separate paediatric EDs). Each site will aim to recruit a minimum of 10 patients and will be limited to a maximum of 60 patients.
 
The sample size will have sufficient power to estimate both the rate of incorrect dosing and use in association with other opioids
 
The rates of incorrect dosing and concomitant opioid use are based on the previous DIASAFE study (DIA002). In that study 14 of 226 subjects (6%) received the incorrect dose and 5 of 226 subjects (2%) received concomitant opioids defined as any other opioids (including any given if Ayendi/diamorphine is insufficient treatment) received from the time of the injury until the subject's discharge from the ED. Regardless of event rate, 400 patients will provide a maximum half-width of the 95% confidence interval (based on a normal approximation) of 4.9%. With this sample size, the half-width of the 95% confidence interval for the incorrect dosage rate is 2.3% and for the opioid usage rate is 1.4%. Thus a sample size of 400 patients provides precise estimates for a range of rates.

POPULATION - INCLUSION CRITERIA:	
The MHRA have requested that no age range is defined in order to capture all data on Ayendi use. Hence data from patients dosed outside the SmPC restrictions will be collected also to provide a comprehensive review of use in clinical practice. Thus any patient who has been prescribed Ayendi as part of routine treatment in the ED is eligible for the study.
 
To be eligible for inclusion into this study the subjects must fulfil all of the following criteria:

	
 1. Patient has been administered Ayendi Nasal Spray by the attending ED Healthcare Professional as part of ED treatment. 2. Parent(s)/legal guardian/adult patient (whichever is applicable) must be able and willing to provide written informed consent before the patient is discharged from the ED. 3. Where applicable, child patients should assent to allow their data to be used for the study.
POPULATION - EXCLUSION CRITERIA:	None
VARIABLES:	
Primary Parameters:
 
 ▶ Rate (%) of doses given (mg/kg) which deviate from the posology as written in the SmPC. ▶ Patients with previous opioid usage immediately prior to Ayendi (%) 
Secondary Parameters:
 
 ▶ Time of administration (including pre-arrival at hospital, if appropriate) ▶ Dose Prescribed (mg/kg) vs Dose Given (mg/kg) ▶ Product strength and Number of sprays given ▶ Diagnosis for which Ayendi was prescribed (% used for off- label indications) ▶ Participating ED practice setting (%) ▶ Administrator (%) ▶ Concomitant medication ▶ Patient demographics (including patients who do not fit within the categories defined in the SmPC). ▶ Adverse events (%)
DATA SOURCES	
The attending ED Healthcare Professional will decide if Ayendi Nasal Spray is the optimum pain relief treatment and will administer the drug as per routine clinical practice as appropriate – this is not part of the study.
 
After Ayendi has been administered but before the patient is discharged from the ED, approved hospital staff (including the direct clinical care team and hospital research staff) will approach the parent(s)/legal guardian/patient (whichever is applicable) to discuss the use of the patient’s data for research purposes. If the parent(s)/legal guardian(s)/patient (whichever is applicable) agrees to the inclusion of the patient’s data in the study, approved hospital staff will transcribe from ED records onto study specific Case Report Forms the following information:
 
 ▶ Demographic data: weight, age, gender ▶ Indication (site and nature of injury/trauma) / diagnosis ▶ Relevant current and ongoing medical history ▶ Concomitant medications taken during the study period ▶ Details (name, position, qualifications, whether training to use Ayendi nasal spray has been undertaken) regarding the Ayendi administrator ▶ Time of dose (if Ayendi administered more than once, time of each separate dose) ▶ Strength and dose of Ayendi prescribed

	
 ▶ Strength and dose administered ▶ Any issues with dosing as per the routine practice in the ED records. ▶ Adverse events that occur prior to discharge/transfer from the ED ▶ Serious Adverse Events that occur prior to discharge/transfer from the ED 
Study-specific information from the informed consent form and the study identification log includes the following:
 
 ▶ Unique subject identifier to identify site and subject number in study ▶ Administration setting ▶ Date of informed consent (subject assent, if applicable) ▶ Confirmation of adherence to inclusion criteria 
This is purely an observational study and no further information will be documented as part of the study. Information not recorded as part of routine clinical practice should not be included in the CRF, even when available – the CRF is not regarded as primary source data.
 
Safety Assessments:
 
Assessments of safety will be performed throughout the time that the patient is in the hospital according to standard ED practice.
 
No further data will be collected regarding the patient once they have left the ED.
 
Adverse event recording
 
Adverse events will be defined as any new diagnosis, any reason for referral to a consultant, any unexpected deterioration in a concurrent illness, any suspected adverse drug reaction, or any complaint which was considered to be of sufficient importance such that it should be recorded in the patient’s medical/nursing notes. These data will be transcribed onto the CRF.
 
Only AEs that are recorded in the patient’s hospital notes as part of routine clinical practice will be recorded in the CRF.
 
Adverse event reporting
 
This is a non-interventional study based on secondary use of data and will be conducted in compliance with GVP Module VIII and VI, where appropriate. As such and in accordance with GVP Module Section VIII.B.6.2 and GVP Module VI Section VI.C.1.2.1., expedited reporting of Serious Adverse Events is not required in this study.
 
All adverse events, including Serious Adverse Events, will be reported in the Clinical Study Report.

STUDY DURATION:
	
Data collection will be requested for the single visit to the ED.


DATA ANALYSIS:
	
This is an observational study of patients post receiving prescribed Ayendi Nasal Spray in EDs in order to assess the utilisation of Ayendi post marketing authorisation approval. Continuous variables will be summarised using descriptive statistics; n, mean, standard deviation, median, minimum and maximum, while categorical variables will be summarised as the number (and percentage) of patients in each category.

	
 ▶ Demographic data will be summarised overall and by weight in accordance with the approved posology categories, and otherwise, as appropriate. ▶ Concomitant medications will be tabulated by weight group along with the current available WHO drug dictionary coding by primary term and generic drug name. ▶ Safety analyses will be simply summarised. ▶ Adverse events will be coded according to the current version of MedDRA.
MILESTONES:	
The study data collection period is estimated to be approximately 12 months from initiation.
 
An interim report will be generated at approximately 6 months.
 
The study report will be available within 12 months of completion of data collection.

DATA SAFETY MONITORING COMMITTEE (DSMC):	None
DATA QUALITY CONTROL:	A minimum 10% sample of CRFs at each participating site will be 100% quality controlled against the source data record.
ADDITIONAL DATA VALIDATION:	
Additional, separate, retrospective case study
 
The MHRA have requested confirmatory retrospective data extraction where data will be collected from a second cohort of patients. Additional summary data will be used, to provide validation for the results of the prospective study, to ensure that no bias has been introduced by the consent process.
 
A minimum of 5 sites will provide retrospective, anonymised data extracted from an additional number of patients who have been dosed with the product. The retrospective data extraction will likely begin towards the end of the prospective study when sufficient data are available. The timing and number of patients will be agreed on a site by site basis. Application for approval of this retrospective data extraction will be made separately.

GUIDANCE DOCUMENTS:	
 ▶ Directive 2001/20/EC of the European Parliament and of the Council of 4 April 2001 on the approximation of the laws, regulations and administrative provisions of the Member States, Official Journal of the European Communities, 1.5.2001; L 121/34-44. ▶ ICH Topic E 6. Guideline for Good Clinical Practice. Step 5, Consolidated Guideline from 01.05.1996. Note for Guidance on Good Clinical Practice (CPMP/ICH/135/95). Jan.1997. ▶ Statutory Instruments (UK Law): SI 2004 No. 1031, 2006 No 1928. ▶ Guidance for the format and content of the protocol of non-interventional post authorisation safety studies EMA/623947/2012 ▶ Guideline on good pharmacovigilance practices (GVP) Module VI – Management and reporting of adverse reactions to medicinal products. EMA/873138/2011 (superseded version) ▶ Guideline on good pharmacovigilance practices (GVP) Module VIII - Module VIII – Post-authorisation safety studies (Rev 1)
STUDY REGISTRATION:	Therakind Limited will make study information available in the EU electronic register of post-authorisation studies (EU PAS Register). The study protocol

	will be entered in the register before the start of data collection. Updates of the study protocol in case of substantial amendments, progress reports, where applicable, and the final study report will be entered in the register (if possible within two weeks after their finalisation).
--	---

5. AMENDMENTS AND UPDATES

None

Number	Date	Section of study protocol	Amendment or update	Reason
-	-	-	-	-

6. MILESTONES

Milestone	Planned date
Start of data collection	Estimated at Q4 2016
End of data collection	Estimated at 12 months post start of data collection
Interim study progress report	Estimated at 6 months post start of data collection
Final report of study results	12 months post end of data collection

7. RATIONALE AND BACKGROUND

Wockhardt UK Limited, in collaboration with Therakind Limited, has developed a new dosage form, specifically for nasal use, of the off-patent product diamorphine hydrochloride for use in children as an analgesic for the relief of acute pain – diamorphine hydrochloride nasal spray (Ayendi Nasal Spray). The device delivers the drug as a very fine mist into the richly vascularised nasal epithelium.

Two studies have been completed in order to support the clinical development of this product, a pharmacokinetic study (DIA001)¹ and a safety study (DIA002)².

On review of the marketing authorisation application by MHRA, it was noted that the safety study (DIA002) highlighted difficulties of administering the product in the Emergency Department. This post-authorisation safety study (PASS) (DIA003) was requested by MHRA to evaluate the practical usage of the product as a treatment in the Emergency Department. The study will assess the patterns of use particularly in relation to aspects that may have an impact on the safety of the product (e.g. co-medication [including other opioids], medication errors). The study will also assess the effectiveness of risk minimisation activities. **The study is**

observational with no intervention – data not recorded as routine clinical practice should not be recorded on the CRF.

Ayendi Nasal Spray is available commercially in two strengths:

- Ayendi 720microgram/actuation Nasal Spray
- Ayendi 1600microgram/actuation Nasal Spray

The product is comprised of diamorphine hydrochloride, freeze dried powder reconstituted with 0.5% preserved saline solution and administered in a nasal spray device, equivalent to 720µg OR 1600µg in each spray.

This will be prescribed and administered in the ED of sites included in the observational study, theoretically in accordance with the approved SmPC.

The study will be conducted in compliance with the protocol, ICH GCP and the applicable regulatory requirement(s).

8. RESEARCH QUESTION AND OBJECTIVES

The purpose of this prospective observational study is to evaluate the practical usage of Ayendi Nasal spray post authorisation in UK Emergency Departments.

8.1 Primary objective

To determine the rates of:

- ▶ Doses given (mg/kg) which deviate from the posology as written in the SmPC.
- ▶ Previous opioid usage immediately prior to Ayendi (%)

8.2 Secondary objectives

- ▶ Time of administration (including pre-arrival at hospital, if appropriate)
- ▶ Dose Prescribed (mg/kg) vs. Dose Given (mg/kg)
- ▶ Product strength and Number of sprays given
- ▶ Diagnosis for which Ayendi was prescribed (% used for off- label indications)
- ▶ Participating ED practice setting (%)
- ▶ Administrator (%)
- ▶ Concomitant medication
- ▶ Patient demographics (including patients who do not fit within the categories defined in the SmPC).
- ▶ Adverse events (%)

9. RESEARCH METHODS

9.1 Study Design

This is an MHRA requested observational, case-only, prospective study into the use of Ayendi Nasal Spray in hospital EDs in order to assess the drug utilisation post marketing authorisation.

No medicinal product will be supplied by the Sponsor; Ayendi will be available already at the hospital pharmacy without reference to this study.

Ayendi will be administered according to clinical need as determined by the attending ED physician – the Sponsor research team will have no influence on which, or even if, patients are prescribed Ayendi.

It is anticipated that Ayendi will be administered to the patient in accordance with the SmPC, although data will be collected on **all** patients who receive Ayendi (where appropriate consent to include their data in the study is obtained) in line with the MHRA requirement for this study (as described in the final assessment report of the marketing authorisation application for Ayendi).

9.1.1 Study Methods

This is purely an observational study. The attending physician will provide routine standard of care and prescribe medicinal products as per hospital standard of care and the patient's requirements – **this is not part of the study.**

In order to provide the potential of obtaining the broadest cohort, consent will be taken **after** the patient has been given the Ayendi Nasal Spray as part of routine clinical practice.

After Ayendi has been administered but before the patient is discharged from the ED, approved hospital staff (including the direct clinical care team and hospital research nurses) will approach the adult patient/parent(s)/legal guardian/patient (whichever is applicable) to discuss the use of the patient's data for research purposes. If the adult patient/parent(s)/legal guardian(s)/patient (whichever is applicable) agrees to the inclusion of the patient's data in the study, approved hospital staff will transcribe the required data from the ED records onto study specific Case Report Forms. Data not recorded as routine practice on the ED records and patient notes should not be recorded on the CRF, even if the information is available.

The **study period** is defined as the time after the patient was administered Ayendi until they are discharged from the ED. After the patient has been treated in the ED, they may be discharged or transferred to a hospital ward. There will be no follow-up information recorded once the patient has been discharged from the ED.

9.2 Study Setting

A minimum of 20 sites across the UK will be included; they will be selected to ensure stratification for teaching and non-teaching hospitals, geographical coverage, department size, experience with diamorphine, and combined or separate paediatric EDs.

9.2.1 Selection of subjects

The MHRA have requested that no age range is defined in order to capture all data on Ayendi use. Hence data from patients dosed outside the SmPC restrictions will be collected also to provide a comprehensive review of use in clinical practice. Thus any patient who has been prescribed Ayendi as part of routine treatment in the ED is eligible for the study.

Inclusion criteria

To be eligible for inclusion into this study the subjects must fulfil all of the following criteria:

1. Patient has been administered Ayendi Nasal Spray by the attending ED Healthcare Professional as part of ED treatment.
2. Parent(s)/legal guardian/adult patient (whichever is applicable) must be able and willing to provide written informed consent before the patient is discharged from the ED.
3. Where possible, child patients should assent to allow their data to be used for the study.

Exclusion criteria

None

[figure not shown]
Withdrawal criteria

Parent(s)/legal guardian(s)/ adult patients (whichever is applicable) may withdraw consent for their data to be included in the study at any time without their care being affected.

No data will be recorded on a CRF for a patient if consent for its use has been withdrawn.

9.3 Study schematic and schedule

A study schematic is presented below.

9.4 Variables and Data Sources

All clinical data to be collected for the study will be transcribed from the ED records onto study specific CRFs by approved hospital staff.

Clinical data which are not recorded routinely in the ED records as part of clinical practice should not be included in the CRF, even if the information is available.

Information transcribed directly from the ED records (where available):

- ▶ Demographic data: weight, age, gender
- ▶ Indication (site and nature of injury/trauma) / diagnosis
- ▶ Relevant current and ongoing medical history
- ▶ Concomitant medications taken during the study period
- ▶ Details (name, position, qualifications, whether training to use Ayendi nasal spray has been undertaken) regarding the Ayendi administrator
- ▶ Time of dose
- ▶ Strength and dose of Ayendi prescribed
- ▶ Strength and dose administered
- ▶ Any issues with dosing
- ▶ Adverse events that occur prior to discharge/transfer from the ED
- ▶ Serious Adverse Events that occur prior to discharge/transfer from the ED

Study-specific information from the informed consent form and the study identification log includes the following:

- ▶ Unique subject identifier to identify site and subject number in study
- ▶ Administration setting
- ▶ Date of informed consent (subject assent, if applicable)
- ▶ Confirmation of adherence to inclusion criteria

In addition to individual Case Record Forms, the following information will be collected by the Clinical Research Associate at each site as part of the site initiation and routine monitoring visits:

- ▶ How Ayendi is generally prescribed
- ▶ How Ayendi is routinely administered
- ▶ How Ayendi administration is recorded in the controlled drug logs
- ▶ Steps taken by the site to minimise dosing error

This is purely an observational study and no further information will be documented as part of the study.

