9.7.2 Statistical analysis

Analysis Populations

Data will be presented for the Safety population, that is, it will include all patients for whom appropriate informed consent was obtained to allow collection of their data.

Data Analysis

Statistical analyses will be performed after all patient data have been collected, protocol deviations reviewed, populations have been agreed and the database has been locked.

Details of all analyses will be included in the SAP.

Continuous variables will be summarised using descriptive statistics; n, mean, standard deviation, median, minimum and maximum, while categorical variables will be summarised as the number (and percentage) of patients in each category.

Demographic data will be summarised overall and by weight in accordance with the approved posology categories, and otherwise, as appropriate.

Concomitant medications will be tabulated by weight group along with the current available WHO drug dictionary coding by primary term and generic drug name.

Safety analyses will be simply summarised.

Adverse events will be coded according to the current version of MedDRA.

Missing, Unused or Spurious Data

The handling of missing, unused and spurious data will be described in the SAP.

Deviations from the Planned Statistical Analyses

Any changes to the planned analysis (as described in the protocol and SAP) will be documented in the statistical and clinical study reports.

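### The data list in section 9.4 has no item for opioids given before Ayendi, so for a primary rate it cannot separate no opioid given from nothing written down

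*Protocol*

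**What the plan says.** Section 8.1 of the protocol names two primary rates. The second is "Previous opioid usage immediately prior to Ayendi", and the abstract lists it as a primary parameter, expressed as a percentage of patients.

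The data that could feed it are fixed in three places:

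- **Section 9.4, Variables and Data Sources.** The patient-level list opens with "Information transcribed directly from the ED records (where available"). Its only medication item is "Concomitant medications taken during the study period". No item concerns opioids before Ayendi. After some site-level information gathered by the monitor, the section rules out any further documentation.
- **Section 9.1.1, Study Methods.** The study period "is defined as the time after the patient was administered Ayendi until they are discharged from the ED". The same section sets the source rule: "Data not recorded as routine practice on the ED records and patient notes should not be recorded on the CRF". Section 9.4 repeats the rule but names the ED records alone, without the patient notes.
- **Section 9.7.2, Statistical analysis.** There is one analysis population: "it will include all patients for whom appropriate informed consent was obtained to allow collection of their data". Missing data are deferred: "The handling of missing, unused and spurious data will be described in the SAP".

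Section 9.9.1 gives the reason for the records-only rule: the prospective data should be comparable in detail with the separate retrospective extraction.

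**The concern.** A records-only study can count a prior opioid only when somebody wrote it down. That is acceptable if the data also show how often the record says nothing. Here they do not. A patient becomes positive through an entry saying an opioid was given. No listed variable distinguishes a record stating that none was given from a record that does not address the question.

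The error, if it occurs, runs one way: under a silent-means-no convention, an unrecorded opioid can lower the rate but cannot raise it. The rate is one of the two main results of a safety study that the regulator requested, with co-medication by other opioids named as a reason for it. A low result could mean little prior opioid use or thin records, and the listed data could not say which.

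**Working it through.** **1. The protocol's own precision figures.** Inputs from section 9.5: n = 400, planning rates 6% (incorrect dose) and 2% (opioids), normal approximation. Half-width = 1.96 × √(p(1 − p)/400).

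- p = 0.50: 4.90 points (stated 4.9)
- p = 0.06: 2.33 points (stated 2.3)
- p = 0.02: 1.37 points (stated 1.4)

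All three reproduce. They describe sampling error only, so the present point does not alter them.

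**2. Can the listed data yield the primary rate?**

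| Needed | Listed in 9.4 |
|---|---|
| Opioid given before Ayendi: drug and time | No such item; the medication item begins after Ayendi |
| Record states that none was given | No such item |
| Record does not say | No such item |

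Medical history and dosing issues are listed, and a prior opioid might be noted there. Neither would show whether an absent entry means none given or not recorded.

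**3. Size if silence counts as no.** Let u be the share of records silent on prior opioids, unrelated to whether one was given. The protocol gives no value, so u from 10% to 50% is an assumption. Taking the 2% planning rate as the true rate, the expected observed rate is 2% × (1 − u).

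The 95% Wilson interval at n = 400 contains 2% when the observed count is 3 to 13. Coverage is therefore P(3 ≤ X ≤ 13) with X binomial(400, 2% × (1 − u)). For the normal-approximation interval the range is 5 to 15.

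| Silent share u | Expected rate | Bias (points) | Wilson coverage | Normal-approximation coverage |
|---|---|---|---|---|
| 0% | 2.0% | 0 | 95.4% | 89.5% |
| 10% | 1.8% | −0.2 | 96.0% | 84.4% |
| 20% | 1.6% | −0.4 | 94.9% | 76.6% |
| 30% | 1.4% | −0.6 | 91.7% | 65.9% |
| 50% | 1.0% | −1.0 | 76.3% | 37.1% |

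The normal-approximation column is below 95% even with complete records, because that interval performs poorly at 2%. Only its fall from 89.5% belongs to this point.

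**4. Size if silent records are identified and left out.** Under the same assumption the expected rate stays at 2% and the cost is precision. With n = 400 × (1 − u) = 360, 320, 280 and 200 for u = 10%, 20%, 30% and 50%, the half-width is 1.45, 1.53, 1.64 and 1.94 points. This option exists only if silence was captured when the record was transcribed.

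**5. Would the retrospective extraction show it?** Section 9.9.1 designs it to detect consent bias, and both data sets are confined to routine records. An opioid missing from the record is missing from both, so the two rates could agree while both are low.

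**The case against.** The strongest objection is that the CRF is not part of the document and 9.4 lists topics, not form fields. The form may already have a prior-opioid question with a not-documented answer. Section 9.7 also commits the SAP to describing how the rate of previous opioid use will be classified. A reader might infer that the form lacks such an answer and that silence is scored as no opioid. The protocol supports neither inference: it shows no response options and states no coding rule. Section 9.7.2 defines who is summarised, not how an undocumented item is coded.

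The records-only rule is also deliberate and explained, and some under-recording is inherent in chart-based research. That stands, and the rule itself is not criticised here.

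The size may be small. At the 2% planning rate, Wilson coverage is about nominal until more than roughly 20% of records are silent, and even at 50% the bias of 1.0 point is below the stated half-width of 1.4. That stands too. Higher true rates would suffer more, but the protocol gives no higher opioid rate.

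Two further inferences lack support. One is that ED records are especially unlikely to hold opioids given before arrival; nothing in the protocol says so. The injury-to-discharge window in 9.5 is the previous study's planning definition, not this primary parameter. The other is that sites with poorer records will look safer, which is possible but not shown.

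Deferral to the SAP does not remove the point. An analysis rule can decide how to treat a recorded not-documented answer, but it cannot recover a distinction that was never transcribed.

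**Conclusion.** The point holds as a gap in what section 9.4 specifies. A primary rate has no corresponding item in the data list, the one medication item covers a different period, and the list does not separate documented absence from silence. Sections 9.1.1 and 9.4 also differ on whether patient notes are a permitted source.

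Downward bias is a conditional consequence, not an established one. It requires that the CRF follow the list as written and that silent records count as negative. Its size depends on a silent share the protocol does not give: under the stated assumptions, from 0.2 points at 10% silent to 1.0 point at 50%, on a true rate of 2%. The case for acting is that, on the listed data, the study could not report that share, while capturing it costs almost nothing.

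**What to change.** - Add to 9.4 a dedicated item on opioid use before Ayendi, transcribed from the record, with three answers: documented given (with drug and time), documented not given, not documented. That a record is silent is itself a fact about the routine record, so the records-only rule is kept.
- Use one wording for the permitted source in 9.1.1 and 9.4, stating whether patient notes are included.
- Report the rate over all patients and over patients with a documented answer, together with the percentage not documented. The first is a lower figure in which silence counts as no. The second is unbiased only if silence is unrelated to opioid use, so it should not be presented as an upper bound.
- Use the same item in the retrospective extraction, so that documentation can be compared between the two data sets.

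The cost is one more CRF item, a little extra tabulation, and a primary rate shown with two denominators. If the CRF already contains such an item, the change reduces to aligning 9.4 with it and stating the denominators.
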